### 5.1.3 Descriptive Endpoints

1. [Redacted]

[Redacted]

[Redacted]

[Redacted]

[Redacted]

**5.1.4 Exploratory Efficacy Endpoints**

1. [Redacted]

[Redacted]

3. [Redacted]

[Redacted]

5.1.5 [Redacted]

1. [Redacted]

[Redacted]

[Redacted]

- [Redacted]
- [Redacted]
- [Redacted]
- [Redacted]

■ [Redacted]

- [Redacted]
- [Redacted]
- [Redacted]
- [Redacted]

5. [REDACTED]
- [REDACTED]
- [REDACTED]
- [REDACTED]
9. [REDACTED]

## 5.2 Safety Endpoints

1. Incidence of adverse events (AEs)
2. Incidence of adverse events of special interest (AESI) overall and by AESI.
3. Absolute and change from baseline to each study visit in blood chemistry parameters
4. Absolute and change from baseline to each study visit in blood hematology parameters
5. Absolute and change from baseline to each study visit for Vital Signs (HR, SBP, DBP, Body Weight) and 12-lead ECG (PR, QRS, QTcF, HR)
6. Incidence of clinically significant findings on abdominal ultrasound

## 6 Statistical Methodology

### 6.1 General Methodology

The following is a list of general reporting conventions:

- Percentages will be based on the number of subjects in the analysis set unless otherwise indicated.

- Categorical variables will be summarized using counts (n) and percentages (%) and will be presented in the form of n (%).
- Percentages will be reported to 1 decimal place.
- Continuous data will be summarized using the mean, standard deviation (SD), median, minimum, 25th and 75th percentiles, maximum, and number of subjects with data.
- Means and medians will be reported at 1 more significant digit than the precision of the data. Standard deviations and confidence intervals will be reported at 2 more significant digits than the precision of the data. Quartiles, minima and maxima will be reported to the same level of precision as the original observations.
- The median will be reported as the average of the 2 middle numbers if the dataset contains even numbers.
- No preliminary rounding should be performed; rounding should only occur after analysis. To round, consider digit to right of last significant digit: if  $< 5$ , then round down; if  $\geq 5$ , then round up.
- All p-values will be reported to 3 decimal places (e.g., 0.XXX). Values  $< 0.001$  will be reported as  $< 0.001$ .

If departures from these general conventions are present in the specific evaluations sections of this SAP, then those conventions will take precedence over these general conventions.

## 6.2 Visit Windows

The following table outlines the analysis visits that data will be mapped to for analysis of data collected during Screening and the DPC period. Data will be analysed using the nominal visit, except in the case of an unscheduled visit that occurs between week 34 and week 36 which is in the place of a missing week 34 visit. These visits will be mapped to the scheduled visit (i.e., week 34). All other unscheduled visits will be listed, but not mapped to a specific analysis visit.

Study Visit	Analysis Visit
Screening 1	Screening 1
Screening 2	Screening 2
Baseline	Baseline
Week 4	Week 4
Week 8	Week 8
Week 12	Week 12
Week 16	Week 16
Week 20	Week 20
Week 24	Week 24
Week 28	Week 28
Week 32	Week 32
Week 34	Week 34
Week 36	Week 36

The following table outlines the analysis visits data will be mapped to for analysis of data collected during the OLE period. Data will be analysed using the nominal visit. All unscheduled visits will be listed, and included in derivations, but not mapped to a specific analysis visit.

Study Visit	Analysis Visit
Baseline	Baseline
Week 4	Week 4
Week 8	Week 8
Week 12	Week 12
Week 16	Week 16
Week 20	Week 20
Week 24	Week 24
Week 36	Week 36
Week 46	Week 46
Week 48	Week 48
Week 60, 72, 84, ... (i.e, every 12 weeks)	Week 60, 72, 84, ... (i.e, every 12 weeks)

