## **1 Introduction**

This Statistical Analysis Plan (SAP) contains a more technical and detailed elaboration of the principal features of the analysis described in the protocol, and includes detailed procedures for executing the statistical analysis. This SAP should be used in conjunction with the protocol. If there are any discrepancies between the protocol and SAP, this SAP will prevail. Any deviations from this SAP that are implemented in the final analysis will be documented with sound clinical and statistical rationale in the Clinical Study Report (CSR). In the event of any changes to the primary endpoints or analyses, these changes will be documented through a protocol amendment, consistent with ICH E9.

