### 5.1.2 Secondary Efficacy Endpoints

1. Proportion of patients who maintain GH response (i.e., GH < 2.5 ng/mL) at week 36, out of those who were responders (i.e., GH < 2.5 ng/mL) on SRL injections at Screening. GH response will be defined using the mean integrated GH value, based on 5 assessments, 30 minutes apart. Patients who discontinue treatment during the DPC period for any reason will be classified as non-responders for the GH response analysis, regardless of their GH values.
2. Time to loss of response: Loss of response is defined as the earliest time when the IGF-1 of 2 consecutive visits is  $> 1 \times \text{ULN}$ , after the patient is treated for at least 2 weeks with 4 capsules per day. The date time of the earliest of the 2 consecutive measurements will be used. To account for patients who prematurely discontinue treatment prior to meeting these criteria, three different approaches will be used (i.e., this endpoint will be defined in three different ways). The three different definitions that will be used are as follows; (A) they will be counted as having had an event (i.e., met the criteria) at the time of treatment discontinuation; (B) they will be censored at the time of their last available assessment, when the patient was known to have not lost response. If there is no post-baseline assessment for response status, the patient will be censored with a time to loss of response of 0; and (C) they will not be censored, but evaluated for response based on the data collected after discontinuation (i.e., as long as the patient is known to be a responder regardless of adherence to treatment. For all three approaches patients who complete the study without meeting these criteria will be censored at their last study visit during the DPC period (i.e., week 36). Although 3 different approaches will be used, only the first approach will be used with respect to determining success. The other 2 approaches will not be considered in the multiplicity adjustment and are considered exploratory.

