3. Time to loss of response: Loss of response is defined as the earliest time when the IGF-1 of 2 consecutive visits is  $> 1.3 \times \text{ULN}$ , after the patient is treated for at least 2 weeks with 4 capsules per day. The date time of the earliest of the 2 consecutive measurements will be used. To account for patients who prematurely discontinue treatment prior to meeting these criteria, three different approaches will be used (i.e., this endpoint will be defined in three different ways). The three different definitions that will be used are the same as those outlined for the endpoint above (endpoint #4). Patients who complete the study without meeting these criteria will be censored at their last study visit during the DPC period (i.e., week 36). Although 3 different approaches will be used, only the first approach will be used with respect to determining success. The other 2 approaches will not be considered in the multiplicity adjustment and are considered exploratory.

4. Proportion of patients who begin rescue treatment prior to and including week 36. The denominator for each group will be all patients randomized to that group. The numerator will be those who start rescue treatment prior to and including week 36.

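### SAP 6.2, read plainly, leaves the repeat and end-of-treatment IGF-1 values out of time to loss of response, which can bias exploratory approaches B and C

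*SAP*

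**What the plan says.** SAP 6.2 sets the DPC rule: "Data will be analysed using the nominal visit, except in the case of an unscheduled visit that occurs between week 34 and week 36". That exception covers only a visit standing in for a missing Week 34. For the rest: "All other unscheduled visits will be listed, but not mapped to a specific analysis visit". The table runs from Screening 1 to Week 36 and has no EOT row.

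The OLE rule in the same section reads: "All unscheduled visits will be listed, and included in derivations, but not mapped to a specific analysis visit".

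SAP 5.1.2 items 2 and 3 define loss of response by IGF-1 at two consecutive visits above 1 × ULN and 1.3 × ULN respectively, after at least 2 weeks on 4 capsules per day. On dating, item 2 says: "The date time of the earliest of the 2 consecutive measurements will be used". Patients who stop treatment before meeting the definition are handled in three ways:

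- **Approach A** counts stopping as an event. It is the only approach used to judge success.
- **Approach B** (exploratory): "they will be censored at the time of their last available assessment, when the patient was known to have not lost response".
- **Approach C** (exploratory): patients are "evaluated for response based on the data collected after discontinuation".

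Item 3 carries these over: "The three different definitions that will be used are the same as those outlined for the endpoint above".

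Protocol 5.2, 5.2.3 and 5.6 call for a second IGF-1 at an unscheduled visit within 2 weeks of any value of 1.3 × ULN or more. Protocol 5.4 has IGF-1 taken at EOT, which may be held apart from a scheduled visit. Protocol 4.6.1 treats rescue as discontinuation of study medication.

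**The concern.** DPC visits are 4 weeks apart through Week 32, and the confirming sample is due within 2 weeks. The value that establishes loss of control and triggers rescue will therefore often be an unscheduled one. If such values are listed but not used, the loss-of-response derivation does not see the evidence on which the patient was rescued.

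Approach B then censors the patient because control was lost, so the censoring is informative. Approach C looks at later data, but by then the patient is back on injections and IGF-1 may have normalised.

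Rescue should be more common on placebo, so the lost events fall mainly there. B and C would understate the difference between arms. They show whether the approach A result depends on counting every discontinuation as an event, and a visit-handling artefact would make them look less consistent with A than the data are.

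**Working it through.** **1. The text.** The DPC and OLE sentences in SAP 6.2 are parallel, but only the OLE sentence says that unscheduled visits enter derivations. Together with nominal-visit analysis and a single named exception, the plain reading is that other unscheduled DPC values are not used. That is an inference; no sentence says they are excluded.

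**2. One constructed patient.** IGF-1 (× ULN): Week 8, 0.98; Week 12, 1.40; unscheduled Week 14, 1.45; rescue at Week 14; normal from Week 16 on injections. Assume 4 capsules per day for at least 2 weeks by Week 12, and the symptom criterion met. The result is the same at both thresholds:

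| Approach | Repeat used | Repeat listed only |
|---|---|---|
| A | event, Week 12 | event, Week 14 |
| B | event, Week 12 | censored, Week 8 |
| C | event, Week 12 | no event, censored Week 36 |

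The loss is not automatic. If a second scheduled on-treatment value is also high, or under C the first scheduled value after rescue is still high, the event stays at its original date.

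**3. The reverse case.** Week 12, 1.35; unscheduled Week 14, 0.95; Week 16, 1.05; no discontinuation. Ignoring the normal repeat creates an endpoint 2 event at Week 12 under A, B and C. Using it gives none.

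**4. Size.** The plan gives no figure to reproduce. The simulation inputs below are assumptions:

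- baseline uniform on 0.65–1.0 × ULN; log-normal placebo escape level reached by Week 8, median 1.3, 1.5 or 1.8 × ULN, log SD 0.15 to 0.35
- within-patient CV 0.10 or 0.20
- symptom criterion met in 50, 70 or 90%
- recovery 4 or 8 weeks after rescue
- a repeat exactly 2 weeks after each scheduled value of 1.3 or more (any dose, or only on 4 capsules)
- 2,500 patients per setting; ranges are minimum to maximum over settings

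The repeat was one of the two qualifying values in 92.7–99.8% of placebo rescues. Rescued placebo patients kept as events in approach B with repeats listed only (100% when repeats are used):

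| Drug stops | >1 × ULN | >1.3 × ULN |
|---|---|---|
| 1 week after confirmation | 4.1–49.1% | 0.7–24.6% |
| 2 weeks after, repeats following any value ≥1.3 | 7.1–66.0% | 6.0–47.9% |
| 2 weeks after, repeats only on 4 capsules | 95.8–100% | 68.3–98.2% |
| next scheduled visit | 94.8–100% | 68.3–98.2% |
| separate EOT sample counts, repeat does not | 95.5–100% | 68.0–98.2% |

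Approach C, listed only: 68.2–100% and 10.6–90.9% with the 1-week stop; 95.3–100% and 68.3–98.2% with the next-visit stop.

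Uptake of repeats also matters. In a similar model with 50% uptake (also an assumption), the repeat was in the qualifying pair in about 46–48% of rescues. Approach B with a 1-week stop then kept 62–68% (>1) and 54–57% (>1.3).

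**5. Trial level.** 25 per arm, median escape 1.3 (placebo) and 1.0 (octreotide), CV 0.15, full uptake, 600 trials. Approach B events at >1.3 × ULN:

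- 1-week stop: placebo 5.9 listed only against 14.7 used; octreotide 2.6 against 5.3. The gap between arms is 5.9 − 2.6 = 3.3 instead of 14.7 − 5.3 = 9.4.
- Next-visit stop: placebo 12.6 against 14.4; octreotide 4.4 against 5.3. The gap is 8.2 instead of 9.1.

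**6. Approach A.** Events were dated 1.3–3.7 weeks later on average. The largest differences in log-rank power were 0.843 against 0.865 (>1) and 0.800 against 0.823 (>1.3), about 2 points. The standard error of one simulated power near 0.82 is √(0.82 × 0.18 / 600) ≈ 0.016, so these differences are close to simulation error.

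**The case against.** The strongest reply is that nothing is excluded. SAP 6.2 is about mapping, and a Kaplan–Meier date needs no mapped visit. SAP 5.1.2 speaks of measurements and date-times. The protocol writes the same rescue rule with visits in one place and assessments in another, and protocol 5.2.3 counts the repeat as the second of two consecutive assessments. Appendix A footnote 14 asks for visits at least 1 week apart, which fits counting a repeat. A rescued patient has by definition two consecutive values of 1.3 × ULN or more, so calling that patient not lost for endpoint 2 would contradict the trial's own record.

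Much of this stands as evidence of intent, and it supports the fix. It does not settle the derivation, because item 2 also says visits and the authors thought the extra words necessary for the OLE. The precedence clause, "If there are any discrepancies between the protocol and SAP, this SAP will prevail", does not settle it either: it applies only where the documents conflict, and whether they do is the open question. SAP 6.3.2, which keeps all reported values, is the outlier rule and is silent on visit handling.

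The reply is also right on size. Full uptake of repeats at exactly 2 weeks is assumed, while protocol 5.2.3 uses both mandatory and optional language. The documents do not say how soon capsules stop after confirmation.

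A reader might infer that the confirmatory results are at risk. The documents do not support that. B and C are outside the multiplicity scheme, and A keeps a rescued patient's event. The primary endpoint classes anyone who stops study medication as a non-responder, and the rescue proportion is a count of rescues over all randomized patients.

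**Conclusion.** The point holds as a gap in wording with a possible bias in two exploratory analyses. The exclusion is implied, not express. If a programmer follows the plain reading, approach B censors some patients because loss of control was confirmed, and approach C may miss them once injections restart.

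The size cannot be determined from the documents. It is small if drug stops at the next scheduled visit, if the EOT sample counts, or if few repeats are taken. It is large if drug stops sooner and repeats are routine. The direction, understating the difference between arms, rests on rescue being more common on placebo.

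For rescued patients, confirmatory approach A changes only in the event date. The reverse case shows that an ignored normal repeat can also create an event, so A is not wholly untouched, but the simulated effect on its power is about 2 points at most. The primary endpoint and rescue proportion are not materially affected. Priority is low; the fix is worth making because it costs almost nothing.

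**What to change.** Before unblinding, add to SAP 5.1.2 items 2 and 3, with a cross-reference in 6.2:

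*For time to loss of response, IGF-1 values from unscheduled and EOT visits in the DPC period are included, in date order, as assessments when identifying 2 consecutive values; for approaches A and B only values taken up to treatment discontinuation (including the EOT sample) are used, and for approach C all DPC values are used.*

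Do not copy the OLE phrase into the DPC sentence as a blanket rule. The primary endpoint averages the last two available assessments, and a blanket rule could bring in repeats that exist only because an earlier value was high. Limiting the change to items 2 and 3 leaves the handling of Weeks 34 and 36 as it is. Approach C needs its own clause because it uses data after discontinuation.

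The cost is one SAP sentence and a cross-reference. No visit, sample or protocol amendment is needed.

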### **6.3 Missing Data, Outliers, Pooling and Multiplicity**

#### **6.3.1 Missing Data**

As the rules for imputation of missing data will differ by endpoint, details on imputation rules for missing data are provided with the description of the endpoint and analytical methods for analysis.

#### **6.3.2 Outliers**

All reported values will be included in the analyses.

#### **6.3.3 Pooling**

Based on the total sample size of the study, and the anticipated number of sites, patients will be pooled across all sites, for all analyses.

#### **6.3.4 Sub Groups**

The following sub-groups will be investigated;

- Region (US sites vs. non-US sites)
- Gender
- Age
- Race

### **6.3.5 Multiplicity**

As there is a single primary endpoint, with a single primary hypothesis test, no adjustment for multiplicity is needed for the primary endpoint/hypothesis test.

To adjust for multiplicity among the secondary endpoints, a fixed testing order will be used. The secondary endpoints will be tested in the pre-specified order as outlined in section 5.1.2, if the primary endpoint is found to be statistically significant. Testing will proceed to the next endpoint if the preceding endpoint is found to be statistically significant at the 5% (two-sided) level. The moment an endpoint is found not to be significant at the 5% (two-sided) level, all remaining endpoints will be considered exploratory, instead of confirmatory. No adjustment for multiplicity will be made for the exploratory endpoints.

The OLE period is viewed as a sub-study. No adjustment for multiplicity for the OLE endpoints will be made.

There will be no statistical analyses of baseline characteristics, demographics or safety endpoints.

## **6.4 Study Sample**

### **6.4.1 Disposition**

A clear accounting of disposition, including the numbers and percentages of patients screened, randomized, completed the DPC period, enrolled into the OLE and completed the OLE will be reported overall and by treatment group. In addition, the primary reasons for screen failure, for early discontinuation of therapy (including those that met pre-defined withdrawal criteria) during the DPC period and early discontinuation during the OLE will be reported overall and by treatment group.

A graphical and tabular summary of the time to discontinuation during the DPC period and during the OLE will also be provided overall and by treatment group.

A summary of the number of patients included in each analysis population will be provided overall and by treatment group.

All subjects who were randomized but withdrew from the study during the DPC period and during the OLE will be provided in a listing, with the reason(s) for discontinuation.

All subjects excluded from the per-protocol set will be listed with the reason(s) for exclusion.

### **6.4.2 Protocol Violations and Treatment Compliance**

For the FAS set, all major protocol violations (e.g., administration of a prohibited concomitant medication, violation of inclusion/exclusion criteria) will be listed by site, including action taken (e.g. discontinuing a subject), if any.

A tabular summary of all major protocol violations will be provided by site, and overall, by treatment group and overall. Major protocol violations will be classified as:

- Violations of inclusion and exclusion criteria
- Receiving the wrong study medication
- Non-compliance with study medication. A patient is defined as non-compliant if the patient took < 75% of the study medication.
- Taking a prohibited medication or receiving a prohibited therapy
- Other

## 6.5 Demographics and Baseline Summaries

Demographic and baseline characteristics will be summarized by treatment group for the FAS set and the OLE set, by treatment group and overall, using descriptive statistics. If the FAS and safety set are different, then summaries will also be presented for the safety set. No statistical hypothesis tests will be performed.

The following continuous demographics data will be summarized:

- Age at screening in years. Age will be derived from the year of birth (year of Study Day 0 – year of birth).
- Weight at screening in kg
- Height at screening in cm
- BMI at screening in kg/m^2. BMI is calculated as weight / height in meters squared.

The following categorical demographics data will be summarized:

- Age: <65 years old, ≥65 years old;
- Gender: Male, Female
- Ethnicity: Hispanic or Latino, Not Hispanic or Latino, Not Reported, Unknown
- Race: Asian, American Indian or Alaskan Native, Black African or African/American, Native Hawaiian or Pacific Islander, White/Caucasian, Other. If more than one race can be selected the patient will be presented in each racial category in the summary table(s).

The following continuous baseline disease characteristics data will be summarized:

- Time from Last Surgery (if applicable)
- Time from Last Radiation (if applicable)
- Average IGF-1 levels (in ULN values) at Baseline (Based on the Average of the 2 assessments within 2 weeks prior to randomization)
- GH levels in mg/mL at Baseline

The following continuous baseline disease characteristics data will also be included for the OLE only:

- Average IGF-1 levels (in ULN values) at Baseline of the OLE (Based on the Average of the last 2 assessments during the DPC period)
- GH levels in mg/mL at Baseline of the OLE (Based on the last value collected during the DPC period)

The following categorical baseline disease characteristics data will be summarized:

- Duration of Acromegaly: <10 years, 10-<20 years, ≥20 years, unknown. Duration will be calculated as the difference in years from the date of diagnosis to date of informed consent.
- Pituitary Tumor Characteristics: Microadenoma, Macroadenoma, Other

- Previous Treatments for Acromegaly any Time in the Past:  
Surgery only (Yes/No)
- Residual Tumor Size: No remnants, < 5mm, 5-10 mm, >10 mm
- Prior Injectable Treatment Octreotide LAR (low, middle and high doses) and Lanreotide (low, middle and high doses)
- Prior Injectable Treatment Overall (low, middle and high doses)
- Prior Injectable Treatment Overall (low vs. middle and high doses)

The following categorical baseline disease characteristics data will also be included for the OLE set only:

- Response in DPC (based on last 3 measures – CR, PR, NR)
- Final Dose in DPC
- Met pre-defined withdrawal criteria in DPC

